20.2.5 Previous COPD treatment

Table 17. Previous COPD treatment according to current treatment on ICS

		Non - ICS	ICS	Total
Previous 2 years	No ICS ICS alone LABA + ICS LABA + LAMA + ICS			
	ICS alone Budesonide Fluticasone propionate			
	LABA + ICS Beclometasone / Formoterol Formoterol / Budesonide Salmeterol / Fluticasone propionate Fluticasone furoate/vilanterol			
	LABA + LAMA + ICS Fluticasone / Umeclidinium / Vilanterol Beclometasone / Formoterol / Glycopyrronium			
Last year	No ICS ICS alone LABA + ICS LABA + LAMA + ICS			
	ICS alone Budesonide Fluticasone propionate			
	LABA + ICS Beclometasone / Formoterol Formoterol / Budesonide			

Document: \\bcnfs02\general\Hdmgener\MEDICAL AFFAIRS 28.02.2017 actualizada\8. SRO ESTUDIOS\RESPIRATORIO\1237-0070 NIS OPTI\11 - Clinical Trial Report\SAP\SAP - V 1.0\SAP OPTI version1.0 29052019.docx

Author:

Version Number: 1.0

Version Date: [29MAY2019]

Template No.: RWI_TP_BIOS0013 Revision 1

Reference: RWI_WI_BIOS0015

Effective Date: 15Jun2018

		Non - ICS	ICS	Total
	Salmeterol / Fluticasone propionate Fluticasone furoate/vilanterol			
	LABA + LAMA + ICS Fluticasone / Umeclidinium / Vilanterol Beclometasone / Formoterol / Glycopyrronium			

Percentages will be calculated over total of patients in each group (100%).

Table 18. Presentation of previous COPD treatment according to current treatment on ICS

		Presentation	Group1	Group2	Total
Previous 2 years	ICS alone				
	Budesonide	 TH: 100 mcg/inh  TH: 200 mcg/inh  TH: 400 mcg/inh			
	Fluticasone propionate	 PCI: 50 mcg/inh  PCI: 125 mcg/inh  PCI: 250 mcg/inh  AH: 100 mcg/inh  AH: 250 mcg/inh  AH: 500 mcg/inh			
	LABA + ICS				
	Beclometasone / Formoterol	 NH: 100/6 mcg/inh  PCI Modulite: 100/6 mcg/inh			
	Formoterol / Budesonide	 TH: 4,5/160 mcg/inh  TH: 9/320 mcg/inh  SM: 4,5/160 mcg/inh  SM: 9/320 mcg/inh  EH: 4,5/160 mcg/inh  EH: 9/320 mcg/inh			
	Salmeterol / Fluticasone propionate	 AH: 50/500 mcg/inh  FP: 50/500 mcg/inh			
	Fluticasone furoate/vilanterol	 EL: 100/25 mcg/inh			
	LABA + LAMA + ICS				
	Fluticasone / Umeclidinium / Vilanterol	 EL: 92/65/22 mcg/inh			
Beclometasone / Formoterol / Glycopyrronium	 PCI: 87/5/9mcg/inh				
Last year	ICS alone				
	Budesonide	 TH: 100 mcg/inh  TH: 200 mcg/inh  TH: 400 mcg/inh			
	Fluticasone propionate	 PCI: 50 mcg/inh			

Document: \\bcnfs02\general\Hdmgener\MEDICAL AFFAIRS 28.02.2017 actualizada\8. SRO ESTUDIOS\RESPIRATORIO\1237-0070 NIS OPTI\11 - Clinical Trial Report\SAP\SAP - V 1.0\SAP OPTI version1.0 29052019.docx

Author:

Version Number: 1.0

Version Date: [29MAY2019]

Template No.: RWI_TP_BIOS0013 Revision 1

Reference: RWI_WI_BIOS0015

Effective Date: 15Jun2018

Copyright © 2018 All rights reserved. The contents of this document are confidential and proprietary to subsidiaries. Unauthorized use, disclosure or reproduction is strictly prohibited.

Holdings Inc. and its

		Presentation	Group1	Group2	Total
		 PCI: 125 mcg/inh  PCI: 250 mcg/inh  AH: 100 mcg/inh  AH: 250 mcg/inh  AH: 500 mcg/inh			
	LABA + ICS				
	Beclometasone / Formoterol	 NH: 100/6 mcg/inh  PCI Modulite: 100/6 mcg/inh			
	Formoterol / Budesonide	 TH: 4,5/160 mcg/inh  TH: 9/320 mcg/inh  SM: 4,5/160 mcg/inh  SM: 9/320 mcg/inh  EH: 4,5/160 mcg/inh  EH: 9/320 mcg/inh			
	Salmeterol / Fluticasone propionate	 AH: 50/500 mcg/inh  FP: 50/500 mcg/inh			
	Fluticasone furoate/vilanterol	 EL: 100/25 mcg/inh			
	LABA + LAMA + ICS				
	Fluticasone / Umeclidinium / Vilanterol	 EL: 92/65/22 mcg/inh			
	Beclometasone / Formoterol / Glycopyrronium	 PCI: 87/5/9mcg/inh			

Percentages (each presentation) will be calculated over the patients receiving each treatment.

Table 19. Doses of previous COPD treatment according to current treatment on ICS

		Doses	Group1	Group2	Total
Previous 2 years	ICS alone				
	Budesonide	200-1600 mcg/24h ___ mcg/___ h ___ mcg/___ h Not available			
	Fluticasone propionate	500 mcg/12h ___ mcg/___ h ___ mcg/___ h Not available			
	LABA + ICS				
	Beclometasone / Formoterol	200/12 mcg/12h ___/___ mcg/___ h ___/___ mcg/___ h Not available			
	Formoterol / Budesonide	9/320 mcg/12h ___/___ mcg/___ h ___/___ mcg/___ h			

Document: \\bcnfs02\general\Hdmgener\MEDICAL AFFAIRS 28.02.2017 actualizada\8. SRO ESTUDIOS\RESPIRATORIO\1237-0070 NIS OPTI\11 - Clinical Trial Report\SAP\SAP - V 1.0\SAP OPTI version1.0 29052019.docx

Author:

Version Number: 1.0

Version Date: [29MAY2019]

Template No.: RWI_TP_BIOS0013 Revision 1

Reference: RWI_WI_BIOS0015

Effective Date: 15Jun2018

Copyright © 2018 All rights reserved. The contents of this document are confidential and proprietary to subsidiaries. Unauthorized use, disclosure or reproduction is strictly prohibited.

Holdings Inc. and its

		Doses	Group1	Group2	Total
		Not available			
	Salmeterol / Fluticasone propionate	50/500 mcg/12h ___/___ mcg/___ h ___/___ mcg/___ h Not available			
	Fluticasone furoate/vilanterol	100/25 mcg/24h XX1/YY1 mcg/ZZ1 h XX2/YY2 mcg/ZZ2 h Not available			
	LABA + LAMA + ICS				
	Fluticasone / Umeclidinium / Vilanterol	92/65/22 mcg/24h ___/___/___ mcg/___ h ___/___/___ mcg/___ h Not available			
	Beclometasone / Formoterol / Glycopyrronium	2 inhal 87/5/9 mcg/ 12h ___/___/___ mcg/___ h ___/___/___ mcg/___ h Not available			
Last year	ICS alone				
	Budesonide	200-1600 mcg/24h ___ mcg/___ h ___ mcg/___ h Not available			
	Fluticasone propionate	500 mcg/12h ___ mcg/___ h ___ mcg/___ h Not available			
	LABA + ICS				
	Beclometasone / Formoterol	200/12 mcg/12h ___/___ mcg/___ h ___/___ mcg/___ h Not available			
	Formoterol / Budesonide	9/320 mcg/12h ___/___ mcg/___ h ___/___ mcg/___ h Not available			
	Salmeterol / Fluticasone propionate	50/500 mcg/12h ___/___ mcg/___ h ___/___ mcg/___ h Not available			
	Fluticasone furoate/vilanterol	100/25 mcg/24h XX1/YY1 mcg/ZZ1 h XX2/YY2 mcg/ZZ2 h Not available			
	LABA + LAMA + ICS				

Document: \\bcnfs02\general\Hdmgener\MEDICAL AFFAIRS 28.02.2017 actualizada\8. SRO ESTUDIOS\RESPIRATORIO\1237-0070 NIS OPTI\11 - Clinical Trial Report\SAP\SAP - V 1.0\SAP OPTI version1.0 29052019.docx

Author:

Version Number: 1.0

Version Date: [29MAY2019]

Template No.: RWI_TP_BIOS0013 Revision 1

Reference: RWI_WI_BIOS0015

Effective Date: 15Jun2018

		Doses	Group1	Group2	Total
	Fluticasone / Umeclidinium / Vilanterol	92/65/22 mcg/24h ___/___/___ mcg/___ h ___/___/___ mcg/___ h Not available			
	Beclometasone / Formoterol / Glycopyrronium	2 inhal 87/5/9 mcg/ 12h ___/___/___ mcg/___ h ___/___/___ mcg/___ h Not available			

Percentages (each dose) will be calculated over the patients receiving each treatment.

20.2.6 Rescue medication

Table 20. Use and type of rescue medication in the previous 2 years according to current treatment on ICS

		Non - ICS	ICS	Total
Use of rescue medication	No Yes Not available in Clinical records			
Rescue medication	SABA (salbutamol) Other treatments Treatment 1 Treatment 2			
Time (days) with salbutamol Within 2 years	Mean (SD) Median (Q1-Q3) Min-Max			
Time (days) with Treatment 1 * Within 2 years	Mean (SD) Median (Q1-Q3) Min-Max			

Percentages will be calculated over total of patients in each group (100%). (*): If there is a high number of other rescue medication, time in treatment will be analyzed for each medication.

Table 21. Use and type of rescue medication in the previous year according to current treatment on ICS

		Group1	Group2	Total
Use of rescue medication	No Yes Not available in Clinical records			
Rescue medication	SABA (salbutamol)			

Document: \\bcnfs02\general\Hdmgener\MEDICAL AFFAIRS 28.02.2017 actualizada\8. SRO ESTUDIOS\RESPIRATORIO\1237-0070 NIS OPTI\11 - Clinical Trial Report\SAP\SAP - V 1.0\SAP OPTI version1.0 29052019.docx

Author:

Version Number: 1.0

Version Date: [29MAY2019]

Template No.: RWI_TP_BIOS0013 Revision 1

Reference: RWI_WI_BIOS0015

Effective Date: 15Jun2018

		Group1	Group2	Total
	Other treatments Treatment 1 Treatment 2			
Time (days) with salbutamol Within previous year	Mean (SD) Median (Q1-Q3) Min-Max			
Time (days) with Treatment 1 * Within previous year	Mean (SD) Median (Q1-Q3) Min-Max			

Percentages will be calculated over total of patients in each group (100%). (*): If there is a high number of other rescue medication, time in treatment will be analyzed for each medication.

20.2.7 Concomitant treatments (ATC code classification)

Table 22. Concomitant treatments according to current treatment on ICS

	Doses	Non - ICS	ICS	Total
Other treatments	No Yes			
Type of treatment	A Alimentary tract and metabolism A10 Drugs used in diabetes A10B Blood glucose lowering drugs, excl. insulins A10BA Biguanides A10BA01 Phenformin A10BA02 Metformin A10BA03 Buformin .. N Nervous System. N02 Analgesics. N02B Other analgesics and antipyretics. N02BE Anilides. N02BE01 Paracetamol (acetaminophen). N02BE01 Paracetamol N02BE03 Phenacetin N02BE04 Bucetin N02BE05 Propacetamol ...			

Percentages will be calculated over total of patients in each group (100%).

Document: \\bcnfs02\general\Hdmgener\MEDICAL AFFAIRS 28.02.2017 actualizada\8. SRO ESTUDIOS\RESPIRATORIO\1237-0070 NIS OPTI\11 - Clinical Trial Report\SAP\SAP - V 1.0\SAP OPTI version1.0 29052019.docx

Author: Version Number: 1.0
Version Date: [29MAY2019]

Template No.: RWI_TP_BIOS0013 Revision 1 Reference: RWI_WI_BIOS0015

Effective Date: 15Jun2018

Table 23. Comorbidities (receiving treatment) according to current treatment on ICS

	Doses	Non - ICS	ICS	Total
Comorbidities receiving concomitant treatment	Total Comorbidity 001 Comorbidity 002			

Percentages will be calculated over total of patients in each group (100%).

20.3 Endpoints

20.3.1 ICS treatment

Table 24. Current treatment on ICS according to the absence or presence of moderate/severe exacerbations in the year prior to the study visit.

ICS treatment	Moderate/severe Exacerbations in the previous year		Total
	No	Yes	
Total patients	N (100%)	N (100%)	N (100%)
Currently non treated with ICS	XXX (XX.X%) [95%CI: XX.X%-XX.X]	XXX (XX.X%) [95%CI: XX.X%-XX.X]	XXX (XX.X%) [95%CI: XX.X%-XX.X]
Currently treated with ICS	XXX (XX.X%) [95%CI: XX.X%-XX.X]	XXX (XX.X%) [95%CI: XX.X%-XX.X]	XXX (XX.X%) [95%CI: XX.X%-XX.X]

*Note: Percentages will be column percentages. Each percentage will correspond to percentage of patients currently treated with ICS, according to the presence of moderate/severe exacerbations in the previous year.

Table 25. Inadequate use of ICS (use of ICS without moderate/severe exacerbations in the previous year) according to clinical and demographic factors (univariate logistic regression analysis)

Variable	Category	Inadequate use of ICS	Odds-Ratio (OR)	p-value
Age	Cont (1 year)	n/N (%)		
Age (cat)	40-49 years	n/N (%)	(ref)	
	50-59 years	n/N (%)		
	60-69 years	n/N (%)		
	70-79 years	n/N (%)		
	80+ years	n/N (%)		

Document: \\bcnfs02\general\Hdmgener\MEDICAL AFFAIRS 28.02.2017 actualizada\8. SRO ESTUDIOS\RESPIRATORIO\1237-0070 NIS OPTI\11 - Clinical Trial Report\SAP\SAP - V 1.0\SAP OPTI version1.0 29052019.docx

Author:

Version Number: 1.0

Version Date: [29MAY2019]

Template No.: RWI_TP_BIOS0013 Revision 1

Reference: RWI_WI_BIOS0015

Effective Date: 15Jun2018

Copyright © 2018 All rights reserved. The contents of this document are confidential and proprietary to Holdings Inc. and its subsidiaries. Unauthorized use, disclosure or reproduction is strictly prohibited.

Variable	Category	Inadequate use of ICS	Odds-Ratio (OR)	p-value
Gender	Male Female		(ref)	
BMI cat	Underweight: BMI< 18.5 kg/m ² Normal weight: 18.5 kg/m ² ≤ BMI≤ 25 kg/m ² Overweight: 25 kg/m ² < BMI≤ 30 kg/m ² Obese: 30 kg/m ² <BMI≤ 35 kg/m ² Severely Obese: BMI> 35 kg/m ²		(ref)	
Smoking habit	Non-smoker Smoker Ex-smoker		(ref)	
History of asthma	No Yes		(ref)	
History of atopy	No Yes		(ref)	
BODEx Index (cat)	Class I Mild: BODEx 0-2 points Class II Moderate: BODEx 3-4 points Class III Serious: BODEx 5-6 points Class IV Very serious: BODEx 7-9 points		(ref)	
COTE Index (cat)	Low risk: COTE index <4 points High risk: COTE index ≥ 4 points.		(ref)	
Time since COPD diagnosis (cat)	0-2 years >2-5 years >5 years		(ref)	
COPD GesEPOC 2017 phenotypes	non-exacerbator, mixed COPD - asthma syndrome (ACOS), exacerbator with emphysema exacerbator with chronic bronchitis		(ref)	
GOLD 2019 spirometric classification	Gold 1 – Mild Gold 2 – Moderate Gold 3 – Severe Gold 4 – Very severe		(ref)	
GOLD 2019 patient groups (A, B, C, D)	Patient A Patient B Patient C Patient D		(ref)	
CAT score (cat)	CAT <10: Low impact of COPD. CAT ≥10: Medium / high impact of COPD		(ref)	
mMRC score	Grade 0 Grade 1 Grade 2 Grade 3 Grade 4		(ref)	
Number of eosinophils (%)	<2% ≥ 2%		(ref)	

Document: \\bcnfs02\general\Hdmgener\MEDICAL AFFAIRS 28.02.2017 actualizada\8. SRO ESTUDIOS\RESPIRATORIO\1237-0070 NIS OPTI\11 - Clinical Trial Report\SAP\SAP - V 1.0\SAP OPTI version1.0 29052019.docx

Author:

Version Number: 1.0

Version Date: [29MAY2019]

Template No.: RWI_TP_BIOS0013 Revision 1

Reference: RWI_WI_BIOS0015

Effective Date: 15Jun2018

Copyright © 2018 All rights reserved. The contents of this document are confidential and proprietary to Holdings Inc. and its subsidiaries. Unauthorized use, disclosure or reproduction is strictly prohibited.

Variable	Category	Inadequate use of ICS	Odds-Ratio (OR)	p-value
Inmunoglobulin E (UI/ml)	<= 100 UI/ml >100 UI/ml		(ref)	
Presence of exacerbations in previous 2 years	None 1-2 exacerbations 3-4 exacerbations 5+ exacerbations		(ref)	
Presence of moderate/severe exacerbations in previous 2 years	None 1-2 moderate/severe exacerbations 3-4 moderate/severe exacerbations 5+ moderate/severe exacerbations		(ref)	
Presence of severe exacerbations in previous 2 years	None 1-2 severe exacerbations 3-4 severe exacerbations 5+ severe exacerbations		(ref)	
Presence of exacerbations in previous year	None 1-2 exacerbations 3-4 exacerbations 5+ exacerbations		(ref)	
Presence of moderate/severe exacerbations in previous year	None 1-2 moderate/severe exacerbations 3-4 moderate/severe exacerbations 5+ moderate/severe exacerbations		(ref)	
Presence of severe exacerbations in previous year	None 1-2 severe exacerbations 3-4 severe exacerbations 5+ severe exacerbations		(ref)	
Antibiotics for COPD exacerbations	No Yes		(ref)	
Oral corticosteroids for COPD exacerbations	No Yes		(ref)	
Type of ICS	ICS alone LABA + ICS LABA + LAMA + ICS			

Inadequate use of ICS: use of ICS without moderate/severe exacerbations in the previous year in patients.

Table 26. Multivariate logistic regression model of inadequate use of ICS (use of ICS without moderate/severe exacerbations in the previous year)

Parameter	Cat	DF	Estimate	Standard Error	Wald Chi-Square	Pr > ChiSq	Exp(Est)
Intercept							

Document: \\bcnfs02\general\Hdmgener\MEDICAL AFFAIRS 28.02.2017 actualizada\8. SRO ESTUDIOS\RESPIRATORIO\1237-0070 NIS OPTI\11 - Clinical Trial Report\SAP\SAP - V 1.0\SAP OPTI version1.0 29052019.docx

Author:

Version Number: 1.0

Version Date: [29MAY2019]

Template No.: RWI_TP_BIOS0013 Revision 1

Reference: RWI_WI_BIOS0015

Effective Date: 15Jun2018

Parameter	Cat	DF	Estimate	Standard Error	Wald Chi-Square	Pr > ChiSq	Exp(Est)
Variable 1							
Variable 2	Cat 2 Cat 3 Cat 4						
...							
Variable n							

Effect	OR Point Estimate	95% Wald Confidence Limits
Variable 1		
Variable 2		
...		
Variable n		

Table 27. Multivariate logistic regression model of inadequate use of ICS (use of ICS without moderate/severe exacerbations in the previous year) by age subgroups

Effect	Patients aged ≤ xx years		Patients aged xx- xx years				Patients aged > xx years	
	OR (95% CI)	p-value	OR (95% CI)	OR (95% CI)	OR (95% CI)	p-value	OR (95% CI)	p-value
Variable 1								
Variable 2								
...								
Variable n								

Document: \\bcnfs02\general\Hdmgener\MEDICAL AFFAIRS 28.02.2017 actualizada\8. SRO ESTUDIOS\RESPIRATORIO\1237-0070 NIS OPTI\11 - Clinical Trial Report\SAP\SAP - V 1.0\SAP OPTI version1.0 29052019.docx

Author: Version Number: 1.0
Version Date: [29MAY2019]

Template No.: RWI_TP_BIOS0013 Revision 1 Reference: RWI_WI_BIOS0015

Effective Date: 15Jun2018

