16.1.3 Primary Analysis of Primary Endpoints

The primary analysis will consist of the proportion of patients, currently on ICS, who did not have or had moderate/severe exacerbation in the year prior to the study visit. The primary analysis will be performed for the FAS.

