16.1.3.1 Current treatment with ICS

Main variable will be presented according to the presence or not of moderate/severe exacerbations in the previous 365 days.

The use of ICS will be analyzed using number of patients in each category and percentages (absolute and relative frequencies) and 95% confidence intervals will be provided based on Wald's (Normal Approximation) method for each group. Percentages will be compared using Chi-Square test or Fisher's Exact test.

Logistic regression will be used to assess the independent contribution of clinical and demographic factors to the estimation of the proportion of patients with COPD who use ICS inadequately. First, univariate and second, multiple logistic regression (MLR) methods will be used to investigate the impact of the following explanatory covariates (patient and disease characteristics) on ICS use.

Potential covariates are:

- Age
- gender
- Smoking history
- Number of exacerbations in the previous year.
- History of asthma (yes/no)
- History of atopy (yes/no)
- COTE index
- COPD GesEPOC 2017 phenotype

Document: \\bcnfs02\general\Hdmgener\MEDICAL AFFAIRS 28.02.2017 actualizada\8. SRO ESTUDIOS\RESPIRATORIO\1237-0070 NIS OPTI\11 - Clinical Trial Report\SAP\SAP - V 1.0\SAP OPTI version1.0 29052019.docx

Author:

Version Number: 1.0

Version Date: [29MAY2019]

Template No.: RWI_TP_BIOS0013 Revision 1

Reference: RWI_WI_BIOS0015

Effective Date: 15Jun2018

Copyright © 2018 All rights reserved. The contents of this document are confidential and proprietary to Holdings Inc. and its subsidiaries. Unauthorized use, disclosure or reproduction is strictly prohibited.

- GOLD 2019 spirometric classifications (1, 2,3, 4)
- GOLD 2019 patient groups (A, B, C, D)
- mMRC score
- CAT - COPD Assessment Test

Backward selection procedures will be applied to generate the final MLR models which consider only covariates in the selection procedure with a p-value <0.1 in the corresponding univariate logistic regression analysis, using inadequate ICS use (yes/no) as response variable. A p-value <0.05 will be used for the covariates to stay in the model in a backward elimination step. Continuous variables can be replaced by categorical variables. Parameters estimated, exp(B) and C95% Wald Confidence Limits for OR will be presented.

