20. TABLES AND FIGURES

20.1 Evaluability

Table 3. Evaluability criteria – Patients in the FAS

		Total
Total included patients (ENR)		
Evaluable patients	Evaluable patients (FAS)	
	Non-Evaluable patients	
Reasons for non-evaluable patients	Inclusion criteria 1	
	Inclusion criteria 2	

ICS Analysis Set (PICAS)		
Safety Analysis Set-ICS		
Safety Analysis Set- BI drug		

Table 4. Other protocol violations occurred in evaluable patients

		Total
Evaluable patients	Evaluable patients (FAS)	
Important protocol violations	ADR (serious or non-serious) or fatal event not notified to BI	
	Any other major or critical Non-Compliance detected during monitoring visit	

Table 5. Main stratification variables

		Total
Total evaluable (FAS)		
Current treatment on ICS	Total	
	No (Non - ICS treatment)	
	Yes (ICS treatment)	
	95% CI for current ICS treatment	
Moderate/severe exacerbations in the previous year	Total	
	No (Without Moderate/severe Exacerbations)	
	Yes (With Moderate/severe Exacerbations)	
	95% CI for presence of moderate/severe exacerbations in the previous year	
Inadequate use of ICS	Total	
	Adherent patients: Adequate use of ICS	

Document: \\bcnfs02\general\Hdmgener\MEDICAL AFFAIRS 28.02.2017 actualizada\8. SRO ESTUDIOS\RESPIRATORIO\1237-0070 NIS OPTI\11 - Clinical Trial Report\SAP\SAP - V 1.0\SAP OPTI version1.0 29052019.docx

Author:

Version Number: 1.0

Version Date: [29MAY2019]

Template No.: RWI_TP_BIOS0013 Revision 1

Reference: RWI_WI_BIOS0015

Effective Date: 15Jun2018

Copyright © 2018 All rights reserved. The contents of this document are confidential and proprietary to Holdings Inc. and its subsidiaries. Unauthorized use, disclosure or reproduction is strictly prohibited.

		Total
	Non-adherent patients: Inadequate use of ICS (use of ICS in patients without moderate/severe exacerbations in the previous year) 95% CI for non-adherent patients (inadequate use of ICS)	

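### Table 25 asks for odds ratios on two predictors that the response excludes by definition, and the exploratory count model (Table 32) keeps GOLD A-D, which is itself built from exacerbations

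*SAP*

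**What the plan says.** **Response.** SAP 16.1.3.1 fits logistic models "using inadequate ICS use (yes/no) as response variable". The titles of Tables 25-27 define that response by exacerbation history; that of Table 25 reads "Inadequate use of ICS (use of ICS without moderate/severe exacerbations in the previous year) according to clinical and demographic factors". The Table 25 footnote repeats the definition: "Inadequate use of ICS: use of ICS without moderate/severe exacerbations in the previous year in patients".

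**Predictors.** Among the Table 25 rows are "Presence of moderate/severe exacerbations in previous year" and "Presence of severe exacerbations in previous year". Each has levels none (reference), 1-2, 3-4 and 5+, under odds ratio and p-value columns. Type of ICS is also a row, without a marked reference level. The candidate list in 16.1.3.1 includes "Number of exacerbations in the previous year", GesEPOC phenotype and GOLD A-D.

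**Cohort.** SAP 16.1.3 says "The primary analysis will be performed for the FAS". SAP 16.1.3.2 then confines the inadequate-use analysis to patients without exacerbations in the previous year and does not state the severity meant. Table 5 gives the label over the whole FAS as "use of ICS in patients without moderate/severe exacerbations in the previous year", but under an adherence heading that SAP 7.2.14 defines differently, by GesEPOC risk and phenotype.

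**Count model.** SAP 16.2.2 models the number of moderate-to-severe exacerbations with the covariates of the primary analysis, leaving out only the previous-year count. SAP 7.2.12 puts a patient in GOLD C or D on two or more exacerbations, or one leading to admission. It gives neither a time window nor a severity.

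**The concern.** A predictor that is part of the response definition cannot say who receives ICS. The two Table 25 rows would yield either no estimate or a software artefact. SAP 16.1.3.2 presents this analysis as part of the main analysis, so the regression tables will be read.

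The count model has the same fault in a less visible form. Removing the previous-year count shows that the authors saw the circularity, but GOLD C/D brings a grouped version of the count back in. The model would converge and print ordinary-looking rate ratios, while C/D absorbs much of the effect of the other factors.

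**Working it through.** **1. The plan's own figure.** Protocol 9.5: 66% non-exacerbators, 61% of them on ICS, N = 900. 0.66 x 0.61 = 0.4026, taken as 40%. The half-width is 1.96 x sqrt(0.4 x 0.6/900) = 0.0320, so 36.8% to 43.2%. This reproduces.

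**2. Expected table in the FAS.** 900 x 0.66 = 594 without a moderate/severe event, and 594 x 0.61 = 362 of them on ICS. 900 - 594 = 306 have at least one event, and all 306 are non-responders by definition. The comparison is 362/594 against 0/306. For the severe row, assuming 5% to 15% of patients had a severe event, the exposed levels hold 0/45 to 0/135.

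**3. Why no odds ratio exists in the FAS.** The intercept is ln(362/232) = 0.445. The exacerbators contribute -306 x ln(1 + exp(0.445 + b)) to the log-likelihood, where b is the log odds ratio:

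| b | contribution |
|---|---|
| -2 | -58.6 |
| -4 | -8.6 |
| -6 | -1.2 |
| -8 | -0.16 |

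It rises without a maximum. In a Newton-Raphson fit the printed result depends on where iteration stops: b = -6.6 with Wald p about 2e-7 at iteration 5, -11.6 with p = 0.45 at iteration 10, -26.6 with p = 0.999 at iteration 25. The likelihood-ratio p is about 6e-93 throughout.

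**4. The 16.1.3.2 cohort.** All 594 patients are at level none in both rows and the other levels are 0/0. The predictor is constant. Type of ICS exists only among ICS users, so there its response is always yes.

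**5. Count model.** Assumptions, none of them from the documents: a factor with 40% prevalence and true rate ratio 2.0; gamma frailty variance 0.5, 1 or 2; 5%, 15% or 30% of events hospitalised; mild events at 0.05 or 0.5 a year. N = 900, with 66% free of moderate/severe events. The outcome is the one-year moderate-to-severe count (Table 32). Ranges of scenario medians:

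| Events counted for GOLD | Rate ratio for C/D | True 2.0 becomes |
|---|---|---|
| Moderate/severe, previous year | 7.7-15.5 | 1.26-1.37 |
| All severities, previous year | 6.4-15.8 | 1.27-1.54 |
| Moderate/severe, two years | 6.6-18.2 | 1.26-1.40 |
| GOLD not in the model | - | 1.93-2.05 |

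The C/D column pools true rate ratios of 1.5 and 2.0.

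In a separate simulation symptoms were unrelated to the count (dispersion 0.5-2, 10% or 30% of events hospitalised). GOLD D against A had a rate ratio of 8.1-15.0 and p < 0.05 in every run. The symptom component alone reached p < 0.05 in 2% to 8% of runs.

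With GOLD removed and exacerbator phenotype kept, the true 2.0 becomes 1.23-1.34 if an exacerbator is a patient with two or more moderate/severe events in the outcome year. The documents give no derivation of phenotype, so this is conditional.

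**6. The logistic candidates in the restricted cohort.** Among 594 patients without moderate/severe events, the previous-year count holds only mild events (SAP 7.2.6.1 counts them). With 61% on ICS and no true association, it reached p < 0.05 in about 3% to 5% of runs at mild rates of 0.05 and 0.5. It behaves normally.

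**The case against.** The strongest reply is that SAP 16.1.3.2 already names the right cohort, that rows of 0/N or 0/0 would be obvious in an n/N column, that p-values are descriptive (8.2), and that the count model is labelled exploratory. GOLD is also only a screened candidate, and its window is not stated. Most of this stands, and it limits the harm. It does not rescue the two rows, which fail in either cohort. Nor would screening remove GOLD, which passed in every null run.

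A reader might infer four stronger things that the documents do not support.

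- **That every odds ratio in Tables 25-27 is distorted.** This would follow from fitting the response in the whole FAS, where it mixes receiving ICS with not exacerbating: a factor with a true ICS odds ratio of 2 that also doubles the exacerbation rate would show 0.85-1.12. But 16.1.3.2 is the specific text and restricts the analysis, and the FAS sentence in 16.1.3 concerns the primary proportion.
- **That the previous-year count and GOLD A-D must leave the logistic models.** In the restricted cohort the count is sound, or merely constant if no exacerbation of any severity is allowed. If GOLD uses previous-year moderate/severe events, C/D is empty and A against B remains estimable; otherwise C/D has patients. Protocol 9.3.3 prespecifies GOLD group.
- **That the failure of the two rows spreads to Tables 26-27.** Neither row is in the 16.1.3.1 candidate list.
- **That the count model is circular whatever GOLD means.** It is circular only where the GOLD and outcome windows overlap.

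**Conclusion.** The point holds in two parts. The two previous-year rows of Table 25 cannot give a usable odds ratio: they are separated in the FAS and constant in the 16.1.3.2 cohort. This follows from the definitions alone; the planning rates only supply the counts. They would be estimable under the GesEPOC meaning of inadequate use, but the titles of Tables 25-27 and the Table 25 footnote rule that meaning out.

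The count model regresses exacerbations on a category of themselves wherever the GOLD window overlaps the outcome window. With GOLD based on previous-year moderate/severe events, C/D takes a rate ratio of about 8-15 and a true 2.0 falls to about 1.3-1.4. For a two-year outcome and a one-year GOLD window the overlap is partial. These sizes rest on the assumed frailty, hospitalised share and factor prevalence, but the direction was the same in every scenario.

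The primary proportion (Table 24) and its interval are not affected. The harm is to the interpretation of the regression tables, and it should be corrected before they are produced.

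**What to change.** 1. **Tables 25-27:** fit them in FAS patients with no moderate/severe exacerbation in the prior 365 days, as 16.1.3.2 intends, with current ICS yes/no as the response. Say that this, not the GesEPOC label of 7.2.14, is meant, and align Table 5.
2. **Table 25:** delete the previous-year moderate/severe and previous-year severe rows. Show type of ICS as n only, without an odds ratio.
3. **SAP 7.2.12:** state the severity and window of the events behind GOLD A-D. GOLD A-D and the previous-year count may stay as logistic candidates in this cohort, and must not be used in a full-FAS fit of this response.
4. **Table 32:** remove both GOLD A-D and exacerbator phenotype from the candidates. Keep mMRC, CAT and spirometric GOLD, which carry symptoms and severity without the count. Record the departure from Protocol 9.3.3 in SAP 4.6, which now reports no changes.

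Cost: SAP text, a few table rows and one entry in 4.6, with no new data. Some rows and covariates are lost. The logistic models use about 594 patients rather than 900, which 16.1.3.2 already implies, with 594 - 362 = 232 in the smaller response class.
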